4.6.6.2. Severe Persistent Hyperglycemia

Summaries of initiation of rescue therapy (see Section 4.1.8.1) in response to severe, persistent hyperglycemia, will be provided by treatment from baseline to Week 30 using SS1 and from baseline to end of treatment period using SS2. If there are enough episodes, a time-to-first-event analysis for the initiation of rescue therapy may be conducted by treatment using a cox proportional regression model (see Section 4.1.5.4).

For patients without an event, the "time-to-event" will be time, in days, from first dose to end of study participation which is either study discontinuation or end of treatment period. A listing of patients initiating rescue therapy will be provided.

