1.2.3. Intervention Groups and Duration

The overall study duration is approximately 60 weeks over 4 required study periods. Table GPGV.1.1 describes the study periods.

 Table GPGV.1.1.
 Intervention Groups and Duration

Study Period	Duration	Intervention
Screening/lead-in	Approximately 4 weeks	
Double-blind, placebo-controlled	30 weeks	5 mg tirzepatide 10 mg tirzepatide, or placebo
Open-label extension on active treatment period	22 weeks	5 mg tirzepatide, or 10 mg tirzepatide
Post-treatment safety follow-up	30 days	

In the 22-week open-label period, participants in 5- and 10-mg arms will continue with current treatment while participants randomized to placebo will initiate treatment at 2.5 mg QW and after 4 weeks, will receive 5 mg of tirzepatide for the remainder of the period.

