4.1. General Considerations

Statistical analysis of this study will be the responsibility of Lilly or its designee. All statistical analyses will be conducted with SAS Version 9.4 or higher unless otherwise stated.

Some analyses and summaries described in this analysis plan may not be conducted if not warranted by data (for example, few events to justify conducting an analysis). Listings of events will be provided in such situations. Additional analyses of the data may be conducted as deemed appropriate without further changes made to the protocol or SAP, even after the final DBL.

All tests of treatment effects will be conducted at a 2-sided alpha level of 0.05/1-sided alpha level of 0.025, unless otherwise stated, and all CIs will be given at a 2-sided 95% level. In statistical summaries and analyses, all data, including those collected during the open-label period, will be analyzed by randomized treatment assignment. In the event of a treatment error, participants will be analyzed according to the treatment they were randomly assigned to.

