4.1.3. End of Study Participation

The end of study participation for a participant will be the earliest of date of death, date of withdrawal from further participation in the study, or date of the safety follow-up visit. For participants considered to be lost to follow-up, end of study participation will be the date of lost to follow-up reported by the investigator. Participant data included in the database after the last date of study participation (date of death, date of early termination, or date of safety follow-up) will be excluded from statistical analyses.

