4.1.5.4. Analysis Relative to Safety Estimand

The analysis related to the safety estimand from double-blind period (baseline to week 30) will be conducted utilizing data in the SS1, and from double-blind, open-label and follow-up periods will be conducted using the data in the SS2. The analysis models for the continuous endpoints are similar to those specified in Section 4.1.5.1 for MMRM, and in Section 4.1.5.2 for ANCOVA.

The analysis of *safety binary endpoints* or other categorical endpoints will be carried out using Fisher's exact test.

Negative binomial regression model will be used for the treatment comparison of discrete count measures if deemed appropriate. The response variable of the negative binomial model will be number of episodes (for example, the hypoglycemic episodes).

For double-blind period, the model will include:

- treatment (placebo, tirzepatide 5 mg, and tirzepatide 10 mg) as a factor
- baseline hypoglycemia incidence as covariate, and
- with log (exposure in days/365.25) as an offset variable.

For overall study period at Week 52 visit, (including double blind and open-label periods), a summary of descriptive statistics will be presented.

A nonparametric empirical model may be used to analyze the event counts if the event counts are low.

Kaplan-Meier method will be used for estimation of cumulative event-free survival rates over time, and Cox proportional hazards regression analysis will be used to compare hazard rates among treatments. The following terms will be included in the model: treatment, stratification factors (baseline age groups and baseline antihyperglycemic medications).

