4.6.6.1. Hypoglycemic Events

Definitions and information on hypoglycemia are provided in Section 8.3.3.1 of Protocol GPGV.

Total hypoglycemia includes any event that meets criteria for documented symptomatic, severe, asymptomatic, or unspecified (that is, missing symptoms or signs, but with a blood glucose, BG, <70 or <54 mg/dL) whether daytime or nocturnal. Those categories that are defined by BG will be analyzed by the BG <70 and <54 mg/dL thresholds separately.

Total hypoglycemia category will have the following 2 subcategories:

- events with BG < 70 mg/dL included, and
- events with BG <54 mg/dL included.

To avoid duplicate reporting, all consecutive BG values <70 mg/dL (3.9 mmol/L) occurring within a 1-hour period may be considered as a single hypoglycemic event.

SS1 will be used for the primary analysis for hypoglycemia during Week 0 through Week 30, and SS2 for Week 0 through end of the treatment period (Week 52).

The incidence of hypoglycemic episodes will be summarized for each treatment group for 0 to 30 weeks, and 0 to the end of the treatment period. The summary includes the number of patients and percent of patients reporting hypoglycemic episodes. Fisher's exact test will be used for treatment comparison.

Counts of hypoglycemia or the rate of incidence of hypoglycemia episodes may be analyzed as described in Section 4.1.5.4 with a negative binomial regression model. The results will also be reported for the subset of participants who have baseline basal insulin use. All these analyses will be conducted excluding data after initiation of new antihyperglycemic therapy.

A listing of the individual hypoglycemic episodes will be presented from baseline to the end of the treatment period using SS2. Additional exploratory analyses may be performed if deemed necessary.

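### The optional Cox comparison of time to first rescue keeps the placebo arm at risk to Week 52, after it has switched to tirzepatide

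*SAP*

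**What the plan says.** SAP 4.6.6.2 plans summaries of rescue initiation over two windows: "from baseline to Week 30 using SS1 and from baseline to end of treatment period using SS2". It then adds an optional model: "If there are enough episodes, a time-to-first-event analysis for the initiation of rescue therapy may be conducted by treatment", using Cox regression as set out in 4.1.5.4. For participants without an event, the time runs "from first dose to end of study participation which is either study discontinuation or end of treatment period". No analysis set is named for this model.

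Other parts of the SAP bear on that sentence:

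- 4.1.5.4 states the purpose of the model: "Cox proportional hazards regression analysis will be used to compare hazard rates among treatments". It gives the Cox model no time window. For event counts, it makes the Week 52 analysis descriptive.
- 4.6.6.1 shows what the end of the treatment period means: "SS2 for Week 0 through end of the treatment period (Week 52".
- 4.1.3 defines the end of study participation differently, as the earliest of death, "withdrawal from further participation in the study, or date of the safety follow-up visit".
- 1.2.3 says that in the open-label period "participants randomized to placebo will initiate treatment at 2.5 mg QW and after 4 weeks, will receive 5 mg of tirzepatide".
- 4.1 says that "all data, including those collected during the open-label period, will be analyzed by randomized treatment assignment".
- 4.1.2 places the safety comparison of tirzepatide with placebo in the double-blind period, on SS1. Section 3 limits SS1 to double-blind data.
- 4.1.4 relabels the placebo arm as Placebo/TZP 5 mg for outputs up to Week 52 and rules out comparing the groups at Week 52.

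**The concern.** The model compares arms, but its only stated censoring rule carries follow-up past the point where the placebo arm ceases to exist. A programmer who follows that sentence would count open-label time on tirzepatide as placebo risk time. The hazard ratio would then mix a placebo-controlled period with one that has no control. If the former placebo participants' rescue hazard moves toward the tirzepatide hazard, the ratio shrinks toward 1 and understates the double-blind contrast.

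Initiation of rescue is a listed additional secondary safety endpoint, outside type I error control. A programmer who instead assumed SS1 would get a different hazard ratio from the same data. A choice of that kind should be settled before the data are seen.

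**Working it through.** **1. The plan's own figures.** The plan gives no event count, hazard ratio or power for this model. Its only sizing figure is 90% power for the primary HbA1c comparison (SAP section 5). With 30 v 60 participants, a difference of 1.1 and an SD of 1.5, 1.1 / (1.5 × √(1/30 + 1/60)) = 3.28. This gives power of 0.907 (normal) or 0.900 (t, 88 df). The figure reproduces and is not touched by this point.

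**2. Which date does the censoring rule mean?**
- It is not Week 30, because 4.6.6.2 sets Week 30 and the end of the treatment period side by side as two separate windows.
- 4.6.6.1 attaches Week 52 to the second.
- The general definition in 4.1.3 does not stop at Week 30 either; it runs to the safety follow-up visit.

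**3. Risk time affected (documents only).** SAP 1.2 gives 30 weeks double-blind plus 22 weeks open-label, 52 in all. For an event-free placebo completer, 22/52 = 42.3% of risk time is on tirzepatide. With censoring at Week 30 it is 0 of 30 weeks.

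**4. Effect on the hazard ratio (illustration; rescue rates assumed).** Take p as the proportion rescued by Week 30 and a constant weekly hazard of −ln(1−p)/30.
- Placebo, p = 20%: 0.2231/30 = 0.00744.
- Tirzepatide, p = 5%: 0.0513/30 = 0.00171.
- True double-blind ratio: 0.00171/0.00744 = 0.23.

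The limiting Cox ratio θ solves ∫[S_T h_T − w(S_T h_T + S_P h_P)]dt = 0. Here w = θS_T/(θS_T + S_P), S_T and S_P are the survival curves weighted 2/3 and 1/3 for the 60 v 30 allocation, and h_T and h_P are the hazards. The fit is unadjusted, pools the two doses and assumes no dropout. After Week 30 the placebo hazard either falls fully to the tirzepatide hazard, falls to the midpoint of the two, or does not fall. Each fall is taken at once or after the 4 weeks on 2.5 mg.

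| Rescued by Week 30 | Censor Week 30 | Week 52, full fall | Full, after 4 wk | Halfway | Halfway, after 4 wk | No fall |
|---|---|---|---|---|---|---|
| 20% v 5% | 0.23 | 0.33 | 0.31 | 0.27 | 0.26 | 0.23 |
| 15% v 3% | 0.19 | 0.28 | 0.26 | 0.22 | 0.22 | 0.19 |
| 30% v 10% | 0.30 | 0.41 | 0.38 | 0.34 | 0.33 | 0.30 |

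Hand check for 20% v 5% with full fall, using events over person-time:
- Mean placebo risk time is 0.20/0.00744 + 0.80 × (1 − e^(−0.00171×22))/0.00171 = 26.9 + 17.3 = 44.2 weeks, of which 39% comes after Week 30.
- Expected placebo events are 30 × (1 − 0.80 × e^(−0.00171×22)) = 6.9.
- The placebo rate is 6.9/(30 × 44.2) = 0.0052, and 0.00171/0.0052 = 0.33.

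Expected events in this example are 6.0 + 3.0 = 9.0 at Week 30. At Week 52 they run from 6.9 + 5.1 = 12.0 (full fall) to 9.6 + 5.1 = 14.7 (no fall).

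**5. Non-constant hazards.** Protocol 8.3.3.2 tightens the rescue threshold to >200 mg/dL from Week 17, so constant hazards are doubtful. As an extreme case, put all double-blind rescue in Weeks 17 to 30 (hazard −ln(1−p)/13) and let that rate continue. For 20% v 5% the Week 52 ratio is then 0.43 (full fall), 0.37 (full fall after 4 weeks) or 0.30 (halfway), against 0.23 at Week 30.

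**The case against.** The best reply is that the default rule already sets the window. Under 4.1.2, unless stated otherwise, comparison with placebo is in the double-blind period on SS1. Section 4.6.6.2 names no set for the Cox model, so SS1 applies, and SS1 has no data after Week 30. The SAP version history supports that intent: it records that a Week 52 model statement was removed from 4.1.5.4 because treatments are not compared at Week 52. This is good evidence of what was meant. It does not settle what was written, because 4.6.6.2 does specify follow-up time for this analysis and points to Week 52.

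Other points carry some weight:

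- The phrase treatment period is used loosely elsewhere in the SAP. Within 4.6.6.2, however, the contrast with Week 30 is clear.
- The conflict with 4.1.4 is less direct than that with 4.1.2, since its sentence speaks of comparison at Week 52. It does follow text on outputs up to Week 52, and the conflict with 4.1.2 stands without it.
- The model is conditional twice over. With about 9 events by Week 30 and five parameters (two for treatment, one for age group, two for background medication), there would be fewer than 2 events per parameter, so it might never be run.
- The listed endpoint is incidence of rescue, which the Week 30 summary serves.
- Every figure beyond 22/52 rests on assumed rates.

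These limit the importance of the point but do not remove the inconsistency.

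**Conclusion.** The concern holds, as a minor point. As written, the censoring rule for the optional Cox model leaves up to 42% of an event-free placebo completer's risk time on tirzepatide, against 4.1.2 and the evident intent of 4.1.4. That share follows from the documents alone.

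The effect on the hazard ratio depends on assumed rescue rates and on how far the placebo hazard falls after the switch. Under constant hazards, a double-blind ratio of 0.23 becomes 0.26 to 0.33 with a partial or full fall, and is unchanged with none. The late-rescue case reaches 0.43. These are illustrations, not estimates. No claim is made about the p-value, which could move either way because follow-up to Week 52 also adds events. The primary endpoint, the key secondary tests and the Week 30 rescue summary are not affected.

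**What to change.** In SAP 4.6.6.2, state that the between-arm Cox model uses SS1. Event-free participants should be censored at the earliest of study discontinuation, first open-label dose, or the end of the double-blind period, taken as the scheduled Week 30 date if that visit is missed. The last term is a safeguard for participants who stop study drug but stay in the study (protocol 7.1). They are meant to attend all visits, but one who misses Week 30 would have neither that visit nor an open-label dose to end follow-up. Report rescue through Week 52 descriptively by treatment sequence, with Placebo/TZP 5 mg shown separately as in 4.1.4. Align the phrase on end of study participation with 4.1.3.

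The cost is a short edit and no new data. The drawback is fewer events in the model, about 9 instead of 12 to 15 in the 20% v 5% example, which may make it less likely to be run.

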4.6.6.3. Pancreatitis

Treatment-emergent adjudicated-confirmed pancreatitis will be considered as AESI. Summaries of adjudicated and investigator-reported pancreatic events will be provided by treatment from baseline to Week 30 using SS1, and from baseline to safety follow-up using SS2 information about searching criteria for AESI is included in Appendix 1.

Pancreatic enzyme assessment

Observed pancreatic enzyme data (p-amylase and lipase) will be summarized by treatment and nominal visit from baseline to Week 30 using SS1, and from baseline to safety follow-up using SS2. The number and proportion of patients with maximum postbaseline pancreatic enzyme values exceeding the following thresholds will be provided by maximum baseline pancreatic enzyme value:

• $(\le 1 \times \text{ULN}, > 1 \times \text{ULN})$, and post baseline: $\le 1 \times \text{ULN}$, and $(>1 \text{ to } \le 3) \times \text{ULN}$, $(>3 \text{ to } \le 5) \times \text{ULN}$, $(>5 \text{ to } \le 10) \times \text{ULN}$, $>10 \times \text{ULN}$.

MMRM model as described in Section 4.1.5.4 will be used to analyze each pancreatic enzyme with a log transformed (postbaseline measure/baseline measure) response variable.

4.6.6.4. Thyroid Malignancies, C-Cell Hyperplasia, and Calcitonin

Thyroid malignancies and C-cell hyperplasia will be considered AESI. TE thyroid disease, C-cell hyperplasia, and neoplasms will be identified using predefined MedDRA HLTs of thyroid neoplasms, and PT of C-cell hyperplasia information about searching criteria for AESI is included in Appendix 1. Summary by treatment and PT within HLT, and listings will be provided from baseline to Week 30 using SS1 and from baseline to safety follow-up using SS2.

Observed calcitonin data will be summarized by treatment and nominal visit from baseline to Week 30 using SS1, and from baseline to safety follow-up using SS2. The number and proportion of patients with a maximum postbaseline calcitonin value exceeding the following thresholds will be provided by maximum baseline calcitonin value (\leq 20 ng/L, \geq 20 ng/L to \leq 35 ng/L, \geq 35 ng/L) and post baseline: \leq 20 ng/L, \geq 20 to \leq 35 ng/L, \geq 35 to \leq 50 ng/L, \geq 50 to \leq 100 ng/L, \geq 100 ng/L.

4.6.6.5. Diabetic Retinopathy Complications

A summary of new or worsening retinopathy will be provided by treatment through Week 30 using SS1, and through Week 52 using SS2:

- An incidence of new diabetic retinopathy or diabetic maculopathy in either eye is defined as a presence of retinopathy or macular edema in either eye in those without any eye disease at baseline according to dedicated fundoscopic exam form or AE reporting.
- An incidence of worsening diabetic retinopathy or diabetic maculopathy in either eye is defined as a shift to worsening severity of eye disease reported in the follow-up fundoscopic exam form or AE reporting compared to baseline.

• The AE will be searched using predefined PTs to identify events consistent with diabetic retinopathy, diabetic macular edema, and related complications. Detailed search criteria can be found in Appendix 1.

A shift table will be presented using SS2 for double-blind and open-label periods for the results from the dilated fundoscopic exams. The table will show the proportions of participants with shifts in retinopathy status from baseline to most severe postbaseline result using categories defined on the eCRF. These are

- no retinopathy
- mild non-proliferative diabetic retinopathy
- moderate non-proliferative diabetic retinopathy
- severe non-proliferative diabetic retinopathy, and
- proliferative diabetic retinopathy.

Results from visual acuity exam reported on the eCRF will be summarized by treatment and by eyes (that is, any eye, left eye and right eye) for baseline and postbaseline visit (Week 52).

4.6.6.6. Hypersensitivity Events

Serious and severe cases of hypersensitivity by pre-defined SMQ search will be considered as AESI. Hypersensitivity reactions and related information reported will be summarized by treatment. Two main analyses are performed:

- potential immediate hypersensitivity: analysis of TEAEs occurring from the start of study drug administration up to 24 hours after the end of study drug administration, and
- potential non-immediate hypersensitivity: analysis of TEAEs occurring more than 24 hours after the end of study drug administration, but prior to subsequent study drug administration.

The AE database will be searched using predefined SMQs to identify events consistent with hypersensitivity events. Detailed searching criteria for hypersensitivity events can be found in a file with location listed in Appendix 1. Summaries of all hypersensitivity reactions will be generated by PT with decreasing frequency by treatment, using SS1 from baseline to Week 30, and using SS2 from baseline to safety follow-up.

4.6.6.7. Injection Site Reactions

Severe and serious injection site reactions will be considered as AESI. Injection site reactions, incidence, and related information via the "Injection Site Reaction" electronic case report form will be summarized by treatment. Information to be summarized including the timing of the reaction relative to study drug administration, and characteristics of the injection site reaction: erythema, induration, pain, pruritus, and edema.

[figure not shown]
Additionally, potential injection site reactions will be searched by MedDRA HLTs of injection site reactions, administration site reactions, and infusion related reactions. Searching criteria for injection site reaction events can be found in Appendix 1. The PT will be used for summary by treatment within each HLT category in decreasing order of incidence.

4.6.6.8. Immunogenicity

4.6.6.8.1. Definitions of Sample ADA Status

At a high level, an individual sample is potentially examined multiple times, in a hierarchical procedure, to produce a sample ADA assay result and potentially multiple cross-reactive antibody assay results and multiple neutralizing antibody (NAb) assay results.

The cut points used, the drug tolerance of each assay, and the possible values of titers are operating characteristics of the assay. Figure GPGV.4.1 details a flow chart that reflects the multitiered testing approach.

Abbreviations: ADA = antidrug antibodies; CP = cut point; GIPR = glucose-dependent insulinotropic polypeptide receptor; GLP-1R = glucagon-like peptide-1 receptor; LY = LY3298176 (tirzepatide); NAb = neutralizing antibodies; nGIP = native glucose-dependent insulinotropic polypeptide; nGLP-1 = native glucagon-like peptide-1; T2 = Tier 2; T4 = Tier 4.

Figure GPGV.4.1. Flowchart of immunogenicity multitiered testing approach.

Table GPGV.4.5 outlines results, as reported from Tier 2a of the multitiered testing approach. Tier 4 results are reported similarly.

Table GPGV.4.5. Sample ADA Assay Results

Sample Laboratory Result	Explanation
Detected	ADA are detected and confirmed.
Not Detected	The raw result as reported from the laboratory indicates not detected. The
	clinical interpretation of such results depends on other factors (see
	Table GPGV.4.6).
NO TEST, QNS, etc.	Sample exists but was unevaluable by the assay.

Abbreviations: ADA = antidrug antibodies; QNS = quantity not sufficient.

It can be the case that the presence of high concentrations of tirzepatide will affect ADA immunoassays. Conversely, high levels of ADA may affect the measurement of tirzepatide concentration. Thus, a tirzepatide drug concentration, assessed from a sample drawn at the same time as the ADA sample, plays a key role in clinical interpretation of a sample when the laboratory result is Not Detected (see Table GPGV.4.6).

Table GPGV.4.6. Sample Clinical ADA Interpretation Results

Sample Clinical Interpretation	Explanation	
ADA Present	ADA assay result is Detected	
ADA Not Present	ADA assay result is Not Detected and simultaneous drug concentration is at	
	a level that has been demonstrated to not interfere in the ADA detection	
	method (ie, drug concentration is below the assay's drug tolerance level).	
	For participants receiving placebo, drug concentration is not assessed and is assumed to be below the assay's drug tolerance level.	
	If drug concentration was planned but is not available for a treatment-period sample, a Not Detected sample will be declared ADA Not present.	
ADA Inconclusive	ADA assay result is Not Detected but drug concentration in the sample is	
	≥ the assay's drug tolerance level, which may cause interference in the ADA	
	detection method.	
ADA Missing	ADA sample not drawn, QNS, not tested, etc., causing there to be no	
	laboratory result reported or the result is reported as "no test."	

Abbreviation: ADA = antidrug antibodies; QNS = quantity not sufficient.

All ADA present samples will be evaluated for cross-reactive GIP (Tier 2b), cross-reactive GLP-1 (Tier 2c), NAb LY (tirzepatide) on GIP-R (Tier 4a), and NAb LY (tirzepatide) on GLP-1R (Tier 4b).

Similar terminology to Table GPGV.4.7 applies for each type of cross-reactive and NAb assay. Importantly, each of these are distinct assays and, in general, have different assay operating characteristics.

The following are considered inconclusive for the NAb result:

• NAb LY on the GIP-R: If the NAb result is not detected and the pharmacokinetic (PK) concentration is ≥ drug tolerance limit of the NAb LY on the GIPR assay,

• NAb LY on the GLP-1R: If the NAb result is not detected and the PK concentration is ≥ drug tolerance limit of the NAb LY on the GLP-1R assay.

For cross-reactive NAb interpretations against native GIP and GLP-1, an *in silico* method utilizing results from Tiers 2b and 2c, Tiers 4a and 4b, and tirzepatide concentrations is introduced. The *in silico* method is outlined in Table GPGV.4.7.

Table GPGV.4.7. In Silico Classification for Cross-Reactive NAb

In Silico Classification	Cross-Reactive ADA Result	NAb Result	Circulating Tirzepatide Level (ng/mL)	In Silico Cross-Reactive NAb Interpretation
Cross-Reactive NAb to nGIP	Tier 2b: "Not detected"	Tier 4a: "Not Detected" or Tier 4a: "Detected," N/A, or Missing	Any value or missing	Not Present
	Tier 2b: "Detected"	Tier 4a: "Not Detected"	< drug tolerance limit of the assay	Not Present
	Tier 2b: "Detected"	Tier 4a: "Not Detected"	≥ drug tolerance limit of the assay	Inconclusive
	Tier 2b: "Detected"	Tier 4a: "Detected"	< drug tolerance limit of the assay	Present
	Tier 2b: "Detected"	Tier 4a: "Detected"	≥ drug tolerance limit of the assay	Present
Cross-reactive NAb to nGLP-1	Tier 2c: "Not detected"	Tier 4b: "Not Detected" or Tier 4b: "Detected," N/A, or Missing	Any value or missing	Not Present
	Tier 2c: "Detected"	Tier 4b: "Not Detected"	< drug tolerance limit of the assay	Not Present
	Tier 2c: "Detected"	Tier 4b: "Not Detected"	≥ drug tolerance limit of the assay	Inconclusive
	Tier 2c: "Detected"	Tier 4b: "Detected"	< drug tolerance limit of the assay	Present
	Tier 2c: "Detected"	Tier 4b: "Detected"	≥ drug tolerance limit of the assay	Present

Abbreviations: ADA = antidrug antibodies; GIPR = glucose-dependent insulinotropic polypeptide receptor; GLP-1R = glucagon-like peptide-1 receptor; N/A = not applicable; NAb = neutralizing antibodies; nGIP = native glucose-dependent insulinotropic polypeptide; nGLP-1 = native glucagon-like peptide-1; Tier 2b = cross-reactive ADA to nGIP; Tier 2c = cross-reactive ADA to nGLP-1; Tier 4a = NAb LY (tirzepatide) on GIPR; Tier 4b = NAb LY (tirzepatide) on GLP-1R.

Note: Only the drug tolerance limits of the Tier 4a and 4b assays are used for in silico classifications as they are lower than the drug tolerance limits of the Tier 2b and 2c assays, respectively.

